
during the open label extension were similar to that observed in the double-blind phase and comparable to placebo.

Hypothesis/Objective

The objective of this study is to collect hypothesis generating data about whether intervention with erenumab is an effective treatment for PTH attributed to mTBI. Participants will receive erenumab when PTH has been present for 35-84 days. Once PTH has been persistent for this period of time, patients may be less likely to remit or improve spontaneously compared to if they were enrolled earlier after PTH onset. Thus, this population of individuals with PTH would be considered in high need of treatment.

Specific Aims/Study Endpoints

Primary endpoint

- Moderate-to-severe headache day frequency measured at weeks 9-12 after administration of first dose of erenumab 140mg vs. frequency of moderate-to-severe headache days during the 4-week baseline phase (BP). A moderate-to-severe headache day is defined as any headache lasting at least 2 hours and which at any point reaches at least moderate intensity.

Secondary endpoints

- Percentage of patients with at least a 50% reduction in headache days during weeks 9-12 after administration of first dose of erenumab 140 mg compared to BP.
- Percentage of patients with chronic headache defined as ≥ 15 headache days during weeks 9-12 after administration of first dose of erenumab 140mg compared to BP.
- Headache Impact Test (HIT-6) at weeks 9-12 after administration of first dose of erenumab 140 mg compared to BP.
- Acute treatment day frequency measured at weeks 9-12 after administration of first dose of erenumab 140mg compared to BP. (Acute treatment day is any day on which an analgesic, triptan, or ergotamine containing medication is taken, or device neuromodulation [e.g. vagal or trigeminal nerve electrical stimulation or single pulse transcranial magnetic stimulation] is administered to relieve headache)

Methods

This is a phase II prospective, open-label clinical trial of a CGRP receptor mAb for treatment of PTH. Of note, this was originally designed as a randomized, placebo-controlled clinical trial. However, recruitment into the clinical trial was slow. Since the estimated total enrollment would

be inadequate for making comparisons between the placebo and erenumab groups, the study was revised to an open-label design.

[figure not shown]

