For patients who are participating in the clinical trial, no preventive therapy for headache should be started. Preventive therapies include drugs, biologics, devices, procedures, and non-pharmacological modalities.

Statistical Plan:

Sample Size- all individuals who qualify for the clinical trial and are interested in participating will be enrolled, up to a maximum of 112 participants. This sample size is empirical and results will be used for hypothesis generation.

Headache Diary - Values for missing calendar day entries in a given month will be imputed by prorating scores of 4-week post-treatment periods with 20–27 days of diary data. For months with less than 10 days of diary data, scores will be estimated by the substitution of the patient's previous 28-day period mean score, multiplied by the ratio of the mean for all patients in the same period and divided by the mean for all patients in the previous period. For post-treatment periods with 10–19 days of diary data, scores were estimated using a mean of both methods.

Outcomes - Efficacy analyses will be conducted in the full analysis set, which includes all subjects (intent-to-treat population) who received at least one dose of study drug and have at least 10 days of efficacy assessments for the primary endpoint measured during weeks 9–12. Safety analyses will be performed in all subjects who receive at least one dose of study drug. The primary and secondary endpoints will be analyzed using a within-person one-sample t-test. Signed rank test will be used for the primary analysis if there is a deviation from normality assumption as assessed by Shapiro Wilk's test. Confidence intervals will be calculated. SAS version 9.4 (SAS Institute, Cary NC) will be used for all statistical analyses.

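### The t interval implied for the paired yes/no endpoint of 15 or more headache days can fall well short of 95% coverage if few patients change status, mostly one way; a paired-proportion interval should be named

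*Combined protocol and SAP*

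**What the plan says.** The Outcomes paragraph of the Statistical Plan gives one method for everything: "The primary and secondary endpoints will be analyzed using a within-person one-sample t-test". The only alternative is tied to the primary: "Signed rank test will be used for the primary analysis if there is a deviation from normality assumption". It then adds "Confidence intervals will be calculated", without a type or a level.

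Under Specific Aims/Study Endpoints, one of the four secondary endpoints is "Percentage of patients with chronic headache defined as ≥ 15 headache days during weeks 9-12", compared with BP. No McNemar, exact or score method is named for it.

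On sample size, the plan enrols "up to a maximum of 112 participants" and says "This sample size is empirical and results will be used for hypothesis generation". Methods explains the open-label redesign by noting that "recruitment into the clinical trial was slow". No expected final number is given, and no rate at which patients are expected to change 15-day status.

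**The concern.** A patient is either at 15 or more headache days or not, once at BP and once at weeks 9-12. The within-person difference therefore takes only three values. When few patients change and most change in the same direction, the sample SD of those differences is poorly estimated. If nobody changes it is zero: the t statistic is 0/0 and the t interval is the single point [0, 0].

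In a study meant to generate hypotheses, the estimate and its interval are what the next trial will use. An interval that claims 95% and delivers much less, or that reports no uncertainty at all, would mislead whoever plans that trial.

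**Working it through.** The documents give no power, alpha, effect size or coverage figure, so there is no stated figure to reproduce.

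**Inputs from the documents:** the t-test for all endpoints; the paired yes/no endpoint; the maximum of 112.

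**Assumptions:** a two-sided 95% t interval; n=20 and n=40 as examples of a small final sample; 5% or 10% of all patients leaving the 15-day group and 0-2% entering it.

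**Formulas.** Let a patients leave and b enter, out of n. The estimated reduction is m = (a - b)/n, with s² = (a + b - n·m²)/(n - 1). The interval is m ± t(0.975, n-1)·s/√n. Coverage is the summed trinomial probability of every (a, b) whose interval contains the true reduction. The chance that nobody changes is (1 - p_leave - p_enter)^n.

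**Results:**

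| Leave / enter | n=20 | n=20, nobody changes | n=20, given at least one changer | n=40 | n=112 |
|---|---|---|---|---|---|
| 5% / 0% | 64.1% | 0.95^20 = 35.8% | 99.95% | 86.8% | 91.9% |
| 5% / 1% | 70.7% | 0.94^20 = 29.0% | 99.6% | 86.9% | 92.7% |
| 10% / 0% | 87.6% | 0.90^20 = 12.2% | 99.7% | 91.4% | 93.2% |
| 10% / 2% | 87.6% | 0.88^20 = 7.8% | 95.0% | 91.0% | 94.2% |

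At n=20, once at least one patient changes, coverage is at or above nominal in all four settings. The shortfall there is the [0, 0] collapse. At n=40 with 5% leaving and none entering, the collapse (0.95^40 = 12.9%) again explains nearly all of the 13.2% of trials that miss. At n=40 with 10% leaving and none entering, nobody changes in only 1.5% of trials, yet coverage given at least one changer is 92.8%, so a separate shortfall remains. The misses are nearly all on one side: the interval lies below the true reduction.

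**Sensitivity:**
- One-way change on a fine grid from 5% to 10%: 64-88% at n=20, 82-95% at n=40, 89-95% at n=112. The tabled n=40 values are therefore points, not bounds.
- One-way change of 1-4%: 18-56% at n=20, 33-80% at n=40.
- Balanced change, 5% and 10% in total: 99.8% and 98.6% at n=20, 98.6% and 95.7% at n=40, with [0, 0] counted as covering a true change of zero.
- 15-20% leaving: mostly 92-96%, with dips. For example, 91.6% at n=40 with 20% leaving and none entering, and 84.4% at n=20 with 16% leaving and none entering.

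**Alternative intervals.** Bonett-Price uses p_a = (a+1)/(n+2), p_b = (b+1)/(n+2) and p_a - p_b ± 1.96·√{[p_a + p_b - (p_a - p_b)²]/(n+2)}. In the four tabled settings it covers about 96-100% at all three sample sizes. The Tango score interval covers 97-100% in the same settings at n=20 and n=40. With no changers, Bonett-Price still gives 1.96·√2/(n+2), that is ±12.6 points at n=20 and ±6.6 at n=40. Tango gives z²/(n+z²), that is ±16.1 and ±8.8 points.

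**Worked example, n=40, 2 leaving, none entering:**
- t interval: m = 0.05, s² = (2 - 0.1)/39 = 0.0487, SE = 0.0349, t = 2.023, giving -2.1 to 12.1 points.
- Bonett-Price: 3/42 - 1/42 = 0.0476, SE = √[(0.0952 - 0.0023)/42] = 0.0470, giving -4.5 to 14.0 points.
- Widths: 18.5 against 14.2 points, a ratio of 1.30.

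**The case against.** The strongest case against is that the damaging scenario is not in the documents. The only sample size is the maximum of 112, where coverage in the tabled settings is 92-94%. Nothing shows that as few as 5-10% will change status. In a 28-day period, anyone at 15 or more headache days who halves them has at most 14 and leaves the group. The Background reports 40% responders on erenumab in chronic migraine. If that carried over, which is an assumption across populations and day definitions, 15% would leave once about 0.15/0.40 = 38% of patients started at 15 or more days. This stands as a limit on the size of the problem. It does not remove it: recruitment was slow enough to force a redesign, and entry requires only 4 moderate or severe headache days, so some participants may start below 15 and cannot leave the group.

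Three stronger readings are tempting and are not supported:
- **That the plan commits to a 64% interval.** The interval type and level are not stated. The t interval is inferred from the named test, and 64% belongs to one assumed setting.
- **That the interval is too narrow whenever few patients change.** Balanced change shows no shortfall, and at n=20 the trouble is almost entirely the visible collapse to [0, 0].
- **That the t-test's low type I error calls for an exact McNemar test.** McNemar is more conservative. With 10% discordant and balanced at n=20, type I error is 1.4% for the t-test, 0.03% for exact McNemar and 0.23% for mid-p. At n=40 with 10% leaving and 2% entering, rejection rates are 30%, 11% and 21%. Type I error is no argument for change here.

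**Conclusion.** The point holds in a limited form. The plan names a method unsuited to a paired yes/no endpoint and leaves the interval unspecified. If a 95% t interval is used, and if 5% or 10% leave with 0-2% entering, coverage is 64-88% at n=20, 87-91% at n=40 and 92-94% at n=112. These figures rest on assumed rates, assumed smaller samples and an assumed interval, and they move erratically between neighbouring settings.

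The importance is low. One of four secondary endpoints is affected, in an uncontrolled study with no decision rule attached. A reader might infer that the primary endpoint or the study's conclusions are compromised; the documents do not support that, since the primary is a headache-day count with its own signed-rank fallback.

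**What to change.** Add one sentence to the Outcomes paragraph: for the endpoint of 15 or more headache days, the change in percentage from BP to weeks 9-12 will be reported with a 95% paired-proportion interval, naming either Tango score or Bonett-Price, in place of the t interval. Give the counts leaving and entering the group beside it. Keep the t-test for HIT-6 and acute treatment days. If a p-value is wanted, choose one consistent with that interval; an exact McNemar test is not recommended because of its loss of power.

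The cost is one sentence and a wider interval when few patients change: -4.5 to 14.0 points instead of -2.1 to 12.1 in the example above, about 30% wider. No new data are needed.

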The criteria for grade 4 in the CTCAE grading scale differs from the regulatory criteria for serious adverse events. It is left to the investigator’s judgment to report these grade 4 abnormalities as serious adverse events. If the severity of an adverse event changes from the date of onset to the date of resolution, the adverse event should be recorded as a single event with the worst severity on the Adverse Event Summary CRF.

Reporting Procedures for Serious Adverse Events

The investigator is responsible for ensuring that all serious adverse events observed by the investigator or reported by the subject that occur after signing of the informed consent through the end of the safety follow-up visit (12 weeks after the last dose of investigational product) are recorded in the subject’s record and are submitted to Data Safety Monitoring Committee (DSMC). All serious adverse events must be submitted to the DSMC within 24 hours following the investigator’s knowledge of the event via the applicable CRF. The investigator is to notify the appropriate IRB/IEC of serious adverse events occurring at the site in accordance with local procedures and statutes. Adverse events that occur during the clinical trial will be reported to Amgen according to the timelines described in the Appendix (“[ISS – Timeframes for Submission of Safety Data to Amgen](#)”).

Data and Safety Monitoring and Annual Reporting to Regulatory Agency

IND safety reports. The DSMB will notify FDA and all participating investigators in an IND safety report of potential serious risks, from clinical trials or any other source, as soon as possible, but in no case later than 15 calendar days after the DSMB determines that the information qualifies for reporting. Qualifications for reporting include:

- *Serious and unexpected suspected adverse reaction.* This includes a single occurrence of an event that is uncommon and known to be strongly associated with drug exposure (e.g., angioedema, hepatic injury, Stevens-Johnson Syndrome; one or more occurrences of an event that is not commonly associated with drug exposure, but is otherwise uncommon in the population exposed to the drug; an aggregate analysis of specific events observed in a clinical trial (such as known consequences of the

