underlying disease or condition under investigation or other events that commonly occur in the study population independent of drug therapy) that indicates those events occur more frequently in the drug treatment group than in a concurrent or historical control group.

- *Findings from other studies.* Investigators will report any findings from epidemiological studies, pooled analysis of multiple studies, or clinical studies whether or not conducted under an IND, and whether or not conducted by the sponsor, that suggest a significant risk in humans exposed to the drug. Ordinarily, such a finding would result in a safety-related change in the protocol, informed consent, investigator brochure (excluding routine updates of these documents), or other aspects of the overall conduct of the clinical investigation.
- *Findings from animal or in vitro testing.* Investigators will report any findings from animal or in vitro testing, that suggest a significant risk in humans exposed to the drug, such as reports of mutagenicity, teratogenicity, or carcinogenicity, or reports of significant organ toxicity at or near the expected human exposure. Ordinarily, any such findings would result in a safety-related change in the protocol, informed consent, investigator brochure (excluding routine updates of these documents), or other aspects of the overall conduct of the clinical investigation.
- *Increased rate of occurrence of serious suspected adverse reactions.* Investigators will report any clinically important increase in the rate of a serious suspected adverse reaction over that listed in the protocol or investigator brochure.
- *Submission of IND safety reports.* Investigators will annually submit each IND safety report in a narrative format or on FDA Form 3500A or in an electronic format that FDA can process, review, and archive. Each notification to FDA will be transmitted to the review division in the Center for Drug Evaluation and Research or in the Center for Biologics Evaluation and Research that has responsibility for review of the IND. Upon request from FDA, the investigators will submit to FDA any additional data or information that the agency deems necessary, as soon as possible, but in no case later than 15 calendar days after receiving the request.

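### The safety section sets a 15-day limit for IND safety reports filed by the DSMB, then has investigators submit each report annually, so timing and filer conflict.

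*Combined protocol and SAP*

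**What the plan says.** The relevant section is headed "Data and Safety Monitoring and Annual Reporting to Regulatory Agency". Its opening paragraph, *IND safety reports*, assigns the duty and the time limit: "The DSMB will notify FDA and all participating investigators in an IND safety report of potential serious risks", as soon as possible "but in no case later than 15 calendar days after the DSMB determines that the information qualifies for reporting". The scope is wide, since it speaks "of potential serious risks, from clinical trials or any other source". The bullets that follow list the kinds of qualifying information: serious and unexpected suspected reactions, findings from other studies, findings from animal or in vitro work, and an increased rate of serious suspected reactions.

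The bullet *Submission of IND safety reports* then says: "Investigators will annually submit each IND safety report in a narrative format or on FDA Form 3500A" (or in an electronic format). It continues: "Each notification to FDA will be transmitted to the review division" responsible for the IND. It ends by requiring extra data that FDA requests to be supplied "as soon as possible, but in no case later than 15 calendar days after receiving the request".

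Three other rules are nearby:

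- The last bullet of the section has investigators notify FDA of unexpected fatal or life-threatening suspected reactions within 7 calendar days of the sponsor's first receipt of the information.
- *Reporting Procedures for Serious Adverse Events* says: "All serious adverse events must be submitted to the DSMC within 24 hours".
- The closing table of timeframes for the manufacturer ties the SUSAR copy to the time of regulatory submission, and lists the US IND Annual Report separately among aggregate reports.

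**The concern.** An IND safety report is the means by which FDA learns of a newly identified serious risk. The section first gives it a firm outer limit of 15 days, then says that each such report is submitted annually. Someone working from the submission bullet, which is where a reader would look for filing instructions, could hold a report for the yearly date and so break the limit in the opening paragraph.

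The filer also changes, from the DSMB in the opening paragraph to the investigators in the submission bullet and the 7-day bullet. With two parties named, each could assume that the other has filed.

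At stake is the timeliness of FDA notice for qualifying information that is not fatal or life-threatening. The manufacturer's SUSAR copy would be delayed with it, because its timing follows the regulatory filing. That would not be a separate breach of the manufacturer's table, which sets no date of its own for SUSARs. The 15-day notice to participating investigators is untouched.

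**Working it through.** The plan has no figure to reproduce. The check sets the rules side by side.

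| Rule | Who acts | Recipient | Limit | Clock starts |
|---|---|---|---|---|
| *IND safety reports*, opening paragraph | DSMB | FDA and participating investigators | 15 calendar days | DSMB's determination |
| *Submission of IND safety reports*, first sentence | Investigators | FDA | Annually | Not stated |
| Same bullet, last sentence | Investigators | FDA | 15 calendar days | FDA's request for more data |
| Fatal or life-threatening bullet | Investigators | FDA | 7 calendar days | Sponsor's first receipt |
| *Reporting Procedures for Serious Adverse Events* | Investigator | DSMC | 24 hours | Investigator's knowledge |

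**Timing.** The first two rows concern the same named document and the same recipient. Two readings are possible.

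1. The annual sentence sets the filing time. It then contradicts the 15-day limit.
2. The annual sentence describes a yearly resubmission of reports already sent. There is then no contradiction, but the text does not say this.

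The wording favours reading 1. The sentence covers each report and prescribes the format of an individual filing. The next sentence treats the filing as a notification to FDA, which is the act that the opening paragraph puts under the 15-day limit.

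**Do the other rules settle it?** No. The 7-day rule covers only unexpected fatal or life-threatening suspected reactions. The 24-hour rule sends events to the DSMC, not to FDA. The 15-day rule in the submission bullet applies only after FDA asks for more data. For all other qualifying information, the only FDA filing times are the two that conflict.

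**Size of the possible delay.** Assume one filing date a year and a determination just after that date.

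- Reading 2: delay past the limit = 0 days.
- Reading 1: longest wait = 365 days; delay past the limit = 365 - 15 = 350 days.

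**Filer.** The opening paragraph names the DSMB, and the submission and 7-day bullets name investigators. An unexpected fatal suspected reaction falls under both the opening paragraph and the 7-day bullet, so two parties are named for the same event, with different clocks. The monitoring body is itself called DSMC in the serious adverse event procedures and DSMB here.

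**The case against.** The best defence is that a reader who applies both rules is late for nothing. The 15-day limit leads the section in absolute terms, while the later bullet is mainly about format and addressee. The section heading promises annual reporting, and the annual sentence is the only annual content beneath it in the text available, which gives reading 2 real support. The US IND Annual Report in the closing table concerns copies to the manufacturer, so it does not show that annual reporting to FDA is described elsewhere. The 15 days for requested data runs from a request, and says little about when a first report is due. The 350-day figure is a constructed worst case. Several safeguards also remain: 24 hours to the DSMC, 7 days to FDA for the gravest reactions, notice to IRBs, and 15 days to participating investigators.

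Much of this stands. Reading 2 cannot be excluded, and the 350 days is an upper bound, not an expected delay. The manufacturer's table and the requested-data rule are weak evidence, and the conclusion does not need them. The heading is also weak evidence, because the table of contents gives it without the word Annual. What the defence cannot explain is why the sentence speaks of each report and its individual filing format. If a yearly resubmission is meant, the protocol still has to say so.

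The body of *Participating Site Responsibilities* was not available for this review and may assign the filing duty. That could answer who files. It would not remove the difference between the two statements in the safety section.

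**Conclusion.** The concern holds. The current text gives the same report two filing times and two filers, and nothing available reconciles them. The filer discrepancy is plain on the page. The timing conflict follows from the natural reading of the annual sentence, and on the alternative reading the sentence is incomplete. The delay past the protocol's own limit ranges from 0 days (annual filing additional) to 350 days (annual sentence followed alone, one filing date a year, determination just after that date). It applies only to qualifying information outside the 7-day rule. This is a drafting inconsistency in safety reporting that should be corrected. It has no bearing on the sample size, endpoints or analyses.

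**What to change.** Reconcile the opening paragraph, the submission bullet and the 7-day bullet in one amendment.

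- **Timing.** Either delete the word annually from the submission bullet, so that each IND safety report follows the 15-day limit already stated, or, if a yearly resubmission is intended, say that it is additional to the 15-day report.
- **Filer.** Name one party responsible for submission to FDA throughout the section, or cross-refer to the section that assigns this duty if there is one. Use one name for the monitoring committee.

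The cost is a wording change and a named party or cross-reference. No new data are collected and no analysis changes.
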